## 6.2 Pre-Study Assessments

Pre-study evaluations are to be conducted within 3 weeks prior to start of protocol therapy. Scans for tumor evaluation must be done within 4 weeks prior to the start of therapy. Pre-study assessments include:

Complete medical history and physical examination (including height and weight)  
ECOG Performance Status (see appendix 11.1)

Laboratory evaluations:

- Hematology: CBC with differential
- Complete Metabolic Panel (plus Mg and Phosphorus)
- TSH/Free T3/Free T4
- ACTH/Amylase/Lipase
- CEA
- Serum or urine pregnancy test in women of childbearing potential (**Note:** pregnancy test to be done within 24 hours of day 1 of treatment)

Concomitant medication(s): All concomitant medications will be recorded.

Tumor evaluation: Contrast computed tomography (CT) of the chest, and either contrasted CT of abdomen and pelvis or MRI of abdomen and pelvis.

Tissue (archival and/or fresh biopsy): Obtain archival tissue from diagnostic regimen for correlative studies if available. If insufficient tissue available, subject must agree to mandatory pretreatment biopsy to participate in the clinical trial.

Stool Specimen: Collect pre-treatment stool specimen from patients as described in

Laboratory manual.

Toxicity evaluation: Use NCI CTCAEv4.03 for notation of any baseline toxicity

### 6.3 Treatment Assessments

#### 6.3.1 D1 of Cycle 1

Focused history and physical examination (including weight)

ECOG Performance Status (see appendix 11.1)

Laboratory evaluations:

- Hematology: CBC with differential
- Complete Metabolic Panel (plus Mg and Phosphorus)
- Blood sample for correlatives
- Serum or urine pregnancy test in women of childbearing potential (**Note**: pregnancy test to be done within 24 hours of day 1 of treatment)

Concomitant medication(s): All concomitant medications will be recorded.

Toxicity evaluation: Use NCI CTCAEv4.03 for notation of any baseline toxicity

Administer Study Medications according to Safety Cohort 1 or 2 schedule as depicted in sections 0 and 4.3.2, respectively.

#### 6.3.2 D15 of Cycles 1 and 2

Focused history and physical examination (including weight)

ECOG Performance Status (see appendix 11.1)

Laboratory evaluations:

- Hematology: CBC with differential
- Complete Metabolic Panel (plus Mg and Phosphorus)

Concomitant medication(s): All concomitant medications will be recorded.

Toxicity evaluation: Use NCI CTCAEv4.03 for notation of any baseline toxicity

Administer Study Medications according to Safety Cohort 1 or 2 schedule as depicted in sections 0 and 4.3.2, respectively

#### 6.3.3 D29 of Cycles 1 and 2

Focused history and physical examination (including weight)

ECOG Performance Status (see appendix 11.1)

Laboratory evaluations:

- Hematology: CBC with differential
- Complete Metabolic Panel (plus Mg and Phosphorus)
- Tumor biopsy (optional): **Applies to cycle 1 days 28-35 only**

Concomitant medication(s): All concomitant medications will be recorded.

Toxicity evaluation: Use NCI CTCAEv4.03 for notation of any baseline toxicity

Administer Study Medications according to Safety Cohort 1 or 2 schedule as depicted in sections 4.3.1 and 4.3.2, respectively

#### 6.3.4 D1 of Cycle 2

Focused history and physical examination (including weight)

ECOG Performance Status (see appendix 11.1)

Laboratory evaluations:

- Hematology: CBC with differential
- Complete Metabolic Panel (plus Mg and Phosphorus)
- TSH/Free T3/Free T4
- ACTH/Amylase/Lipase
- CEA
- Serum or urine pregnancy test in women of childbearing potential (within 24 hours of dosing with study medications)
- Blood sample for correlative studies

Concomitant medication(s): All concomitant medications will be recorded.

Toxicity evaluation: Use NCI CTCAEv4.03 for notation of any baseline toxicity

Administer Study Medications according to Safety Cohort 1 or 2 schedule as depicted in sections 0 and 4.3.2, respectively

#### 6.3.5 D1 of Cycle 3-N

Focused history and physical examination (including weight) /

ECOG Performance Status (see appendix 11.1)

Laboratory evaluations:

- Hematology: CBC with differential
- Complete Metabolic Panel (plus Mg and Phosphorus)
- TSH/Free T3/Free T4
- ACTH/Amylase/Lipase
- CEA
- Serum or urine pregnancy test in women of childbearing potential (within 24 hours of dosing with study medications)
- Blood sample for correlative studies

Concomitant medication(s): All concomitant medications will be recorded.

Tumor evaluation: Contrasted computed tomography (CT) of the chest, and either contrasted CT of abdomen and pelvis or MRI of abdomen and pelvis on cycles 3, 5, 7, etc. **Note:** Repeat tumor imaging every 12 weeks (+/- 1 week).

Stool Specimen: Collect stool specimen from patients as described in Laboratory manual +/- 7 days from Day 1 of Cycle 3 only.

Toxicity evaluation: Use NCI CTCAEv4.03 for notation of any baseline toxicity

Administer Study Medications according to Safety Cohort 1 or 2 schedule as depicted in sections 4.3.10 and 4.3.2, respectively

#### 6.3.6 D15 of Cycles 3-N

Focused history and physical examination (including a weight) / **Note:** after 6 cycles completed, only include assessment by physician if clinical signs and symptoms warrant MD consult

ECOG Performance Status (see appendix 11.1)

Laboratory evaluations:

- Hematology: CBC with differential
- Complete Metabolic Panel (plus Mg and Phosphorus)

Concomitant medication(s): All concomitant medications will be recorded.  
Toxicity evaluation: Use NCI CTCAEv4.03 for notation of any baseline toxicity  
Administer Study Medications according to Safety Cohort 1 or 2 schedule as depicted in sections 4.3.1 and 4.3.2, respectively

### 6.3.7 D29 of Cycles 3-N

Focused history and physical examination (including a weight) / **Note**: after 6 cycles completed, only include assessment by physician if clinical signs and symptoms warrant MD consult

ECOG Performance Status (see appendix 11.1)

Laboratory evaluations:

- Hematology: CBC with differential
- Complete Metabolic Panel (plus Mg and Phosphorus)

Concomitant medication(s): All concomitant medications will be recorded.  
Toxicity evaluation: Use NCI CTCAEv4.03 for notation of any baseline toxicity  
Administer Study Medications according to Safety Cohort 1 or 2 schedule as depicted in sections 4.3.1 and 4.3.2, respectively

## 6.4 Post-Treatment/Follow-up Assessments

### 6.4.1 End of treatment

Focused history and physical examination (including weight)

ECOG Performance Status (see appendix 11.1)

Laboratory evaluations:

- Hematology: CBC with differential
- Complete Metabolic Panel (plus Mg and Phosphorus)
- TSH/Free T3/Free T4
- ACTH/Amylase/Lipase
- CEA
- Serum or urine pregnancy test in women of childbearing potential
- Blood sample for correlative studies

Concomitant medication(s): All concomitant medications will be recorded.  
Toxicity evaluation: Use NCI CTCAEv4.03 for notation of any baseline toxicity.  
**Note**: Subjects who experienced a grade 3 or 4 event or SAE during the treatment phase will be contacted every 2 weeks until the event is resolved or deemed irreversible by the investigator.

### 6.4.2 30-day follow up

Focused history and physical examination (including weight)

Laboratory evaluations:

- Serum or urine pregnancy test in women of childbearing potential

Concomitant medications

Toxicity evaluation: Use NCI CTCAEv4.03 for notation of any baseline toxicity.  
**Note**: Subjects who experienced a grade 3 or 4 event or SAE during the treatment phase will be contacted every 2 weeks until the event is resolved or deemed irreversible by the investigator.

#### 6.4.3 100-day follow up

Survival and Toxicity evaluation: Use NCI CTCAEv4.03 for notation of any baseline toxicity. **Note:** Subjects who experienced a grade 3 or 4 event or SAE during the treatment phase will be contacted every 2 weeks until the event is resolved or deemed irreversible by the investigator.

#### 6.4.4 Long-term follow up

Subsequent long-term follow-up visits should occur per standard of care, defined as every 90 days thereafter (+/- 15 days) for up to 3 years or until death (whichever is first) and may be conducted via telephone, medical record check, and/or via clinic visit. These visits will be limited to history of any subsequent cancer treatments, an assessment of any SAE's considered to be possibly or probably related to study treatment until resolution, and survival status.

#### 6.5 Correlative Studies Procedures

Blood samples will be collected for correlative studies on D1 of each cycle and at the end of treatment visit. Collection details will be provided in the study laboratory manual.

Stool specimens will be collected during screening and on approximately Cycle 3 Day 1 (see 6.1 for details on timing of collection). Collection details will be provided in the study laboratory manual.

#### **Handling of Biospecimens Collected for Correlative Research**

Biospecimens collected for this study will be stored in the Lineberger Comprehensive Cancer Center (LCCC) Tissue Procurement Facility (TPF), or if needed, in a secure off-site storage facility. All biospecimen samples will be obtained in accordance with procedures outlined in the LCCC 1632 Study Laboratory Manual and stored in containers with controlled access. Each sample will be assigned a unique code number and no identifiable personal health information (PHI) will be on the specimen label. Information about the subject's disease will be linked to the specimens stored in the repository database. TPF-associated research staff, LCCC Bioinformatics staff who support the TPF database and the LCCC Data Warehouse, and researchers with IRB-approval for access to PHI for each subject in this study will be able to link specimens to relevant medical information. Some results from laboratory analyses that occurred during the subject's participation in the clinical study may also be included. This information may be important for understanding how the subject's cancer developed and responded to treatment.

All the planned correlative research studies will be performed by laboratories affiliated with UNC-Chapel Hill (for additional details please consult the laboratory manual).

#### **Storage Time:**

The biospecimen will be used first and foremost for research purposes outlined within the confines of this protocol. Samples will be discarded/destroyed after relevant data are collected for this study,

unless consent was obtained from the subject to use tissue for other research purposes (e.g., TPF consent form was signed by the subject). In this circumstance, there is no time limit on how long biospecimens may be stored.

- The investigator must agree to abide by policies and procedures of the TPF facility and sign a letter of research agreement for ethical and appropriate conduct of their research that utilizes specimens obtained from the TPF facility (e.g., Use of leftover specimens will require a protocol outlining the research plan for biospecimen use).

### **Compliance Statement**

Biospecimen collection for this study will be conducted in full accordance to all applicable University of North Carolina (UNC) Research Policies and Procedures and all applicable Federal and state laws and regulations including 45 CFR 46, and the Health Insurance Portability and Accountability Act (HIPAA) Privacy Rule. Any episode of noncompliance will be documented.

The investigators will perform the study in accordance with this protocol, will obtain consent and assent (unless a waiver is granted), and will report unexpected problems in accordance with The UNC IRB Policies and Procedures and all federal requirements. Collection, recording, and reporting of data will be accurate and will ensure the privacy, health, and welfare of research subjects during and after the study.

### **6.6 Assessment of Safety**

Any subject who receives at least one dose of study therapy on this protocol will be evaluable for toxicity. Each subject will be assessed periodically for the development of any toxicity according to the Time and Events table. Toxicity will be assessed according to the NCI CTCAEv4.03.

### **6.7 Assessment of Efficacy**

Efficacy will be assessed per RECIST 1.1 Criteria in the next section and by irRECIST as described in Section 6.7.5.1.

#### **6.7.1 Assessment of Disease-Tumor Measurement Based on RECIST 1.1**

See the international criteria proposed by the Response Evaluation Criteria in Solid Tumors (RECIST) Committee, version 1.1 (Eur J Cancer 45;2009:228-247) for additional details on RECIST1.1.

Measurable disease will be defined as the presence of at least one measurable lesion that can be accurately measured in at least one dimension with the longest diameter a minimum size of:

- $\geq 10$ mm by CT scan (CT scan slice thickness no greater than 5 mm)
- 10mm caliper measurement by clinical exam (lesions which cannot be accurately measured with calipers should be recorded as non-measurable).
- 20 mm by chest x-ray.

For malignant lymph nodes to be considered pathologically enlarged and measurable, a lymph node must be  $\geq 15$ mm in short axis when assessed by CT scan (CT scan slice thickness recommended to be no greater than 5mm). At baseline and in follow-up, only the short axis will be measured and followed.

All other lesions, including small lesions (longest diameter  $< 10$ mm or pathological lymph nodes with  $\geq 10$  to  $< 15$  mm short axis) as well as truly non-measurable lesions, will be considered non-measurable. Lesions considered truly non-measurable include: leptomeningeal disease; ascites; pleural/pericardial effusion; inflammatory breast disease; lymphangitic involvement of skin or lung, abdominal masses/abdominal organomegaly identified by physical exam that is not measurable by reproducible imaging techniques.

All measurements should be recorded in metric notation, using calipers if clinically assessed. All baseline evaluations should be performed as close as possible to the treatment start and never more than 4 weeks before the beginning of the treatment. The same method of assessment and the same technique should be used to characterize each identified and reported lesion at baseline and during follow-up. Imaging based evaluation should always be done rather than clinical examination unless the lesion(s) being followed cannot be imaged but are assessable by clinical exam. Clinical lesions will only be considered measurable when they are superficial and  $\geq 10$  mm diameter as assessed using calipers (e.g. skin nodules). For the case of skin lesions, documentation by color photography including a ruler to estimate the size of the lesions is recommended.

### **6.7.2 Baseline Documentation of Target and Non-Target Lesions**

All measurable lesions up to a maximum of 5 lesions total (and a maximum of two lesions per organ) representative of all involved organs should be identified as target lesions and will be recorded and measured at baseline.

Target lesions should be selected on the basis of their size (lesions with the longer diameter), be representative of all involved organs, but in addition should be those that lend themselves to reproducible repeated measurements.

A sum of the diameters (longest for non-nodal lesions, short axis for nodal lesions) for all target lesions will be calculated and reported as the baseline sum diameters. If lymph nodes are to be included in the sum, only the short axis is added into the sum. The baseline sum diameters will be used as reference to further characterize the objective tumor response of the measurable dimension of the disease.

All other lesions (or sites of disease) including pathological lymph nodes should be identified as non-target lesions and should also be recorded at baseline. Measurements are not required, and these lesions should be followed as “present” or “absent”, or in rare cases “unequivocal progression”.

### 6.7.3 Evaluation of Target Lesions using RECIST 1.1 Criteria

**NOTE:** In addition to the information below, also see section 4.3.2 in the international criteria proposed by the Response Evaluation Criteria in Solid Tumors (RECIST) Committee, version 1.1 (Eur J Cancer 45;2009:228-247) for special notes on the assessment of target lesions.

Complete response (CR)—Disappearance of all target lesions. Any pathological lymph node (LN) (whether target or non-target) must have decreased in short axis to <10mm.

Partial response (PR)—At least a 30% decrease in the sum of the LD of the target lesions taking as reference the baseline sum LD.

Progressive Disease (PD)—At least a 20% increase in the sum of the LD of the target lesions taking as reference the smallest sum LD recorded since the treatment started including baseline if that is the smallest on study. In addition to the relative increase of 20%, the sum must also demonstrate an absolute increase of at least 5mm. The appearance of one or more new lesions also constitutes PD.

Stable disease (SD)—Neither sufficient shrinkage to qualify for PR nor sufficient increase to qualify for PD taking as references the smallest sum LD since the treatment started.

### 6.7.4 Evaluation of Non-Target Lesions using RECIST 1.1 Criteria

Complete response (CR)—Disappearance of all non-target lesions and normalization of tumor marker levels. All LN must be non-pathological in size (<10mm short axis).

Non-complete response (non-CR)/non-progression (non-PD)—Persistence of one or more non-target lesion(s) or/and maintenance of tumor marker level above the normal limits.

Progressive disease (PD)—Appearance of one or more new lesions and/or unequivocal progression of existing non-target lesions.

**NOTE:** Any progressive disease as defined by RECIST1.1 in subjects that are asymptomatic without signs or symptoms of impending visceral crisis SHOULD be confirmed by repeat scan to rule out "tumor flare" (pseudoprogression) related to immune response. In these subjects and per MD discretion, study therapy should be continued in these subjects until the repeat scan is performed approximately 4 weeks but no more than 6 weeks later. If PD is confirmed, subjects will be withdrawn from study. If tumor flare confirmed, subjects may continue therapy as per protocol. Subjects that have clear progressive disease as defined by RECIST 1.1 should be withdrawn from treatment and a repeat scan is not necessary.

**6.7.4.1 Evaluation of Best Overall Response** - The best overall responses for both RECIST 1.1 and irRECIST are defined as the best response achieved across all time points prior to progression (for example, a subject who has SD at first assessment, PR at second assessment, and PD on last assessment has a best overall response of PR). Please Note: In the case of SD, measurements must have met the SD criteria at least once after study entry at a minimum interval of 12 weeks from initiation of treatment.

The best overall response will be defined according to the following table:

Overall Response First Time Point	Overall Response Subsequent Time Point	BEST Overall Response
CR	CR	CR
CR	PR	SD, PD, or PR 
CR	SD	SD provided minimum criteria for SD duration met, otherwise, PD
CR	PD	SD provided minimum criteria for SD duration met, otherwise, PD
CR	NE 	SD provided minimum criteria for SD duration met, otherwise, NE 
PR	CR	PR
PR	PR	PR
PR	SD	SD
PR	PD	SD provided minimum criteria for SD duration met, otherwise, PD
PR	NE 	SD provided minimum criteria for SD duration met, otherwise, NE 
NE	NE 	NE 

 If a CR is truly met at first time point, then any disease seen at a subsequent time point, even disease meeting PR criteria relative to baseline, makes the disease PD at that point (since disease must have reappeared after CR). Best response would depend on whether minimum duration for SD was met. However, sometimes 'CR' may be claimed when subsequent scans suggest small lesions were likely still present and in fact the subject had PR, not CR at the first time point. Under these circumstances, the original CR should be changed to PR and the best response is PR.

 NE=inevaluable

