### 2.4.2 Secondary Endpoints

**2.4.2.1** The best overall responses for both RECIST 1.1 and irRECIST are defined as the best response achieved across all time points prior to progression (for example, a subject who has SD at first assessment, PR at second assessment, and PD on last assessment has a best overall response of PR). Please Note: In the case of SD, measurements must have met the SD criteria at least once after study entry at a minimum interval of 12 weeks from initiation of treatment.

**2.4.2.2** The immune-related response rate is defined as the percentage of subjects with unresectable refractory *KRAS/NRAS/BRAF* wild-type MSS mCRC who achieve a CR+PR by 12 weeks to panitumumab/nivolumab/ipilimumab or panitumumab/nivolumab therapy per irRECIST criteria. (See section 6.7.5.1)

**2.4.2.3** Assessment of immune-related PFS is defined as starting from the first day of treatment or Day 1 (D1) until the event of disease progression as defined by irRECIST, or death from any cause in subjects with unresectable refractory *KRAS/NRAS/BRAF* wild-type MSS mCRC (See section 6.7.5.1). Any subject that has not had a documented event at the time of analysis will be censored. Assessment of PFS (as defined by RECIST 1.1) is defined from D1 of treatment until the event of disease progression occurs or death from any cause in subjects with unresectable refractory *KRAS/NRAS/BRAF* wild-type MSS mCRC. Any

October 01,,  
2020

subject that has not had a documented event at the time of analysis will be censored.

- 2.4.2.4 OS is defined as the time from D1 of treatment until death from any cause. Any subject that has not died by the analysis date will be censored.
- 2.4.2.5 The duration of response as defined by RECIST 1.1 will be defined as the time elapsed from first scan documenting partial response or complete response until the event of disease progression occurs. Any subject that has not had a documented progression at the time of analysis will be censored. The duration of response as defined by irRECIST will be defined as the time elapsed from first scan documenting partial response or complete response until the event of disease progression occurs. Any subject that has not had a documented progression at the time of analysis will be censored.
- 2.4.2.6 Treatment-related adverse events will be assessed per NCI-CTCAE v4.03.

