#### 4.6 Duration of Therapy

Subjects should continue protocol therapy as described until:

- Disease progression (Note: treatment should continue until progression is confirmed by repeat scan approximately 6 weeks later to rule out pseudoprogression based on investigator discretion)
- Inter-current illness prevents further administration of treatment
- Unacceptable adverse event(s)

- Subject decides to withdraw from the study, OR
- General or specific changes in the subject's condition render the subjects unacceptable for further treatment in the judgment of the investigator.

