**6.7.5 Other Efficacy Parameters (Immune Response Criteria)**

**6.7.5.1 Evaluation of Response by irRECIST**

Secondary objectives of this study involve assessment of ORR and PFS based in immune response criteria as outlined below (see Guidelines for the evaluation of immune therapy activity in solid tumors: immune-related response criteria. Wolchok JD et al. Clin Cancer Res 2009;15(23):7412-20, Nishino et al. Clin Cancer Res 19(14):3936-43, and Bohnsack O. et al., *Adaptation of the immune related response criteria: irRECIST*. Annals of Oncology (2014) 25 (suppl\_4): iv361-iv372. 10.1093/annonc/mdu342, 2014).

irRECIST criteria are based on irRC criteria (Wolchok et al) adapted for unidimensional measurement as outlined by Nishino et al. The adaptation described by Bohnsack et al. further aligns irRECIST to allow for assessment of

baseline non-target lesions and new non-measurable lesions and discusses the impact of those lesions on the overall tumor response assessment. The adaptation by Bohnsack et al. allows for evaluation of subjects with non-target disease only and subjects in the adjuvant setting (not applicable for this study in subjects with metastatic disease).

Overall response using the irRECIST is based on tumor burden as follows:

irCR	Complete disappearance of all lesions (whether measurable or not, and no new lesions) Lymph nodes must decrease to < 10 mm in short axis. Confirmation of response is not mandatory.
irPR	Decrease in tumor burden $\geq 30\%$ in TMTB relative to baseline confirmed by a consecutive assessment at least 4 weeks after first documentation, non-target lesions are irNN, and no equivocal progression of new non-measurable lesions.
irSD	Not meeting criteria for irCR, irPR, in absence of irPD
irPD	Increase in tumor burden $\geq 20\%$ increase and minimum 5 mm absolute increase in TMTB compared to nadir, or irPD for non-target or new non-measurable lesions confirmed by a repeat, consecutive assessment no less than 4 weeks from the date first documented
irNN	No target disease was identified at baseline and at follow-up the subject fails to meet criteria for irCR or irPD.

irNN = irNon-CR/Non-PD

TMTB = Total measurable tumor burden

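### Sections 4.6, 6.7.4 and 6.7.5.1 time the scan that confirms progression differently, so a repeat scan slightly before 4 weeks can end treatment without confirming irPD

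*Combined protocol and SAP*

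**What the plan says.** Three places set the timing of the scan that confirms progression.

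- **Section 4.6** (Duration of Therapy), in its note on pseudoprogression: "treatment should continue until progression is confirmed by repeat scan approximately 6 weeks later", subject to investigator discretion.
- **Section 6.7.4**, in its NOTE on asymptomatic subjects with RECIST 1.1 progression: "study therapy should be continued in these subjects until the repeat scan is performed approximately 4 weeks but no more than 6 weeks later". It then adds: "If PD is confirmed, subjects will be withdrawn from study".
- **Section 6.7.5.1**, in the irPD row: a rise in total measurable tumor burden of at least 20% and 5 mm, "or irPD for non-target or new non-measurable lesions confirmed by a repeat". The row then requires that assessment to come at least 4 weeks after first documentation.

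The endpoint definitions depend on these rules. Section 2.4.2.3 runs immune-related PFS "until the event of disease progression as defined by irRECIST, or death from any cause" and adds: "Any subject that has not had a documented event at the time of analysis will be censored". Section 2.4.2.5 ends irRECIST duration of response at progression only, and death is not an event there. Section 8.4 plans Kaplan-Meier curves, medians and 95% confidence intervals for both endpoints.

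**The concern.** One repeat scan has two jobs. Under 6.7.4 it decides whether treatment stops. Under 6.7.5.1 it decides whether an irRECIST progression has occurred. If the timing rules differ, the same pair of scans can be confirmed progression for stopping treatment and unconfirmed for immune-related PFS.

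The plan does not correct this later. The Time and Events table (6.1) has no tumor measurement at end of treatment or in follow-up, and sections 6.4.1 to 6.4.4 list no imaging. Sections 2.4.2.3 and 2.4.2.5 say neither how an unconfirmed irPD is handled nor on what date such a subject is censored. A progression seen on two consecutive scans may then be recorded as a later death or as no event. Either way, immune-related PFS, and irRECIST duration of response in responders, look longer than they were. Without a rule, early confirming scans would have to be adjudicated after the data are seen, in an open-label trial.

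**Working it through.** The plan gives no figure for this point, so the check compares the rules and then counts days.

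**1. The timing rules in days (4 weeks = 28 days, 6 weeks = 42 days)**

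| Section | Target | Lower limit | Upper limit |
|---|---|---|---|
| 4.6 | about day 42 | none stated | none stated |
| 6.7.4 | about day 28 | none stated | day 42 |
| 6.7.5.1 (irPD) | none | day 28 | none stated |

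A scan a few days before day 28 fits 6.7.4, fails the irPD minimum and does not fit 4.6. A scan just after day 42 fits 4.6 and the irPD minimum but breaks the 6.7.4 limit. Days 28 to 42 satisfy both 6.7.4 and 6.7.5.1.

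**2. One subject followed through**

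Progression is seen on day 85, and the repeat scan 26 days later (85 + 26 = day 111) still shows it. Under 6.7.4 progression is confirmed and the subject is withdrawn. Under 6.7.5.1, where confirmation is required, 26 < 28, so irPD is not confirmed. No further protocol scan follows. Immune-related PFS then ends at death, which section 4.7 allows to be captured for up to 3 years after treatment, or is censored. If the subject had responded, irRECIST duration of response is censored.

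**3. Two readings of the irPD row**

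- *Broad:* the confirmation clause covers every route to irPD. The subject in step 2 then has no irPD, whichever lesions grew.
- *Narrow:* it covers only non-target and new non-measurable lesions. A sufficient rise in measurable burden is then irPD without confirmation, and the early scan costs no event. The problem remains for non-target progression and new non-measurable lesions.

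**4. Illustrative day counts**

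No window is stated for this repeat scan. Two windows can be borrowed from section 6.1: +/- 3 days (general visits, unless otherwise specified) and +/- 1 week (12-weekly imaging). Share short of 4 weeks = permitted days before day 28 / all permitted days up to day 42.

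- +/- 3 days: days 25 to 42 are 42 - 25 + 1 = 18 days. Days 25 to 27 fall short: 3/18 = 17%.
- +/- 1 week: days 21 to 42 are 42 - 21 + 1 = 22 days. Days 21 to 27 fall short: 7/22 = 32%.
- If the permitted window and the irPD minimum shared a lower limit, the count would be 0.

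These count calendar days. They are not expected proportions of scans or subjects.

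**The case against.** The strongest reply is that this is a missing lower limit with little practical effect. Sections 6.7.4 and 6.7.5.1 can both be met on any of 15 days (28 to 42), and a scan near 6 weeks, as in 4.6, always meets the irPD minimum. The affected group is narrow. The subject must be asymptomatic, be kept on therapy at the physician's discretion, be rescanned before day 28, and have an irPD that needs confirmation. For duration of response the subject must also have responded. Death still counts as an immune-related PFS event. Much of this stands and limits the size of the point. It does not remove it, because 6.7.4 read alone permits the early scan and nothing later repairs it.

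Three stronger readings are tempting, and the documents do not support them.

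- *That 43% or 47% of 4-week repeat scans could not confirm irPD.* These come from 3/7 (days 25 to 31) and 7/15 (days 21 to 35). They borrow windows not stated for this scan, leave out permitted days up to day 42, and treat scans as evenly spread over days.
- *That an early scan always leaves no irPD.* This holds only on the broad reading of the irPD row.
- *That such a subject never has an immune-related PFS event.* Death from any cause is one.

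Section 6.7.4 also says that subjects with clear progression "should be withdrawn from treatment and a repeat scan is not necessary". Irrespective of timing, irPD cannot be confirmed by a repeat scan in them. That gap is separate and possibly wider. The present point concerns subjects who do have the repeat scan.

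**Conclusion.** The inconsistency is real and can be read directly from the three sections. A repeat scan slightly before 4 weeks fits 6.7.4 and ends participation as confirmed progression, but cannot confirm irPD wherever 6.7.5.1 requires confirmation. The likely effect is upward bias in immune-related PFS, through an event delayed to death or through censoring, and in irRECIST duration of response, through censoring. Only these secondary estimates are at risk. The primary RECIST 1.1 ORR does not use irPD.

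The number of subjects affected, and so the size of the bias, cannot be derived from the documents. The 17% and 32% of permitted days are illustrations that assume a borrowed visit or imaging window applies. The conclusion itself needs only that 6.7.4 states no lower limit. How far it reaches depends on which reading of the irPD row is intended.

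**What to change.** 1. Reconcile sections 4.6, 6.7.4 and 6.7.5.1 so that every repeat scan that complies with the protocol can also confirm irPD. The interval is for the sponsor to choose, because it also sets how long therapy continues past apparent progression.
2. State in 6.7.5.1 whether the confirmation requirement covers all irPD or only non-target and new non-measurable lesions.
3. Pre-specify in 2.4.2.3 and 2.4.2.5 how a progression is counted when its confirming scan came before 4 weeks. One option is to count it as an irPD event dated at first documentation, with a sensitivity analysis under the strict 4-week rule. Give the censoring date that applies under the strict rule.

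Cost: a few phrases and one small extra analysis. No scan is added.
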